CIEDs include pacemakers, implantable cardiac defibrillators (ICDs), and cardiac resynchronisation devices (CRT). NICE guidelines (National Institute for Health and Care Excellence) recommend CRT device implantation as a *treatment option* for HF patients with prolonged QRS interval on electrocardiogram and an ejection fraction of 35% or less (37). CRTs have been shown to improve symptoms and slow progression of HF in randomised control trials (RCT) (38, 39). The MIRACLE study (38) (an RCT of 453 patients with moderate to severe HF randomised to CRT versus medical therapy) demonstrated CRT patients experienced a median change in 'distance walked in 6 minutes' of +39m at 6-month follow up (median: +39m, 95% CI +26 to +54, compared to control median: +10m 95% CI 0 to +25, where CI = confidence interval). Evidence suggests the additional endurance effect of CRTs is diminished by 12 weeks of implantation (40), thus data from this time period will be excluded from analysis as PA data may not represent normal behaviour. This will also allow time for the

patient to recover from the procedure, and allow the device time to synchronise its settings. It is unclear how pacemaker or ICD implantation would affect PA, however one could expect some positive impact through better control of symptoms, or perhaps a psychological 'safety-net' for a more active lifestyle. Although some devices with tight pacing settings may limit exertion. We expect this impact to be very small.

Validity of frailty assessments

The Fried phenotypic based frailty assessments are well validated in the general population. We estimate over half of the patients recruited into the PATTERn study will have some degree of HF. One domain of frailty that may be less reliable in a HF cohort is weight loss – as this may fluctuate with fluid status. Significant weight loss within the criteria is defined as over 10% body weight in the preceding four years (or a measured BMI $< 18.5 \text{ kg/m}^2$). These criteria would not tend to capture patients whom have lost weight simply due to diuresis, therefore we do not anticipate this will alter validity of results. The Fried criteria have been used in a number of studies which include participants with HF (19, 41). The original validation study itself included patients with HF, who represented 4.5% of the original Cardiovascular Health Study cohort (42). Therefore, this assessment has validity in this context.

Generalisability of results

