By the nature of this study, participants are limited to those with a compatible CIED i.e. have some form of cardiac disease (the majority HF and/or conduction disorders). Cardiovascular disease is a fundamental pillar of ageing, lying on the spectrum of physiological frailty – inherent, and relevant to all older people (43). Therefore, on balance we do believe this population sample is generalisable to an older population with comparable functional status and degree of frailty. This study will be looking at temporal pattern analysis, using this population as a cohort of older people with a common age-associated long-term condition (heart disease). There is no reason to expect this group of patients would behave any differently with regard to PA and major health events compared with any other older patient group. Therefore we believe these results will be of interest out with the cardiac community.

Sample Size Calculations

Using data from previous analyses (21, 22) sample size calculations have been performed based on the Kesley and Fleiss formulas for 'cohort studies', using exposure = low/decline in PA and outcome = NEHA within 6 weeks. We considered a relative risk (RR) of 2.5-3 to be clinically significant in terms of a PA trigger signifying increased risk of NEHA. Sample size estimate thus = **150** participants (using inputs: 95% significance, 80% power, RR 2.5-3, output: 88 – 198, see *Table 1*).

Table 1: Sample size calculations

Variables	Option 1	Option 2	Option 3	Option 4
Two-sided significance level (1-alpha)	95	95	95	95
Power (1-beta, % chance of detecting):	80	80	90	90
Percent of Unexposed with Outcome:	17	17	17	17
Percent of Exposed with Outcome:	43	51	43	51
RR	2.5	3	2.5	3
Ratio of sample size, unexposed/exposed:	4.4	4.4	4.4	4.4
Sample size: Kesley	133	81	177	108
Sample size: Fleiss	145	88	198	121

The SENSE HF study (enrolling adult patients with chronic, stable HF, 6 months follow-up) captured 224 'unscheduled hospital visits' in 132 patients over 659 patient years, i.e. an annual rate of 34%. (44) Using this as a guide, with a sample size of 150 (150 patient years) we would expect to capture approximately 51 NEHA episodes from retrospective data collection.

Study Objectives

1. Describe the relationship between PA and NEHAs in an older CIED cohort
2. Describe daily variability of PA in an older CIED cohort
3. Describe the relationship between PA and NEHAs, and examining whether frailty moderates this relationship

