Stroke/TIA	
 • Self-report • Coded on electronic medical records

	
• Brain imaging demonstrating previous ischaemic or haemorrhagic event
--	--

Withdrawal from Study

All participant derived data will be collected on the day of consent, bar the occasional case where a participant wishes to take the questionnaire home and post in back at a later date. Given the short period of time each participant will be actively enrolled in the study, it is highly unlikely a withdrawal of consent will occur. In the event of withdrawal of consent, a consent withdrawal form will be used to document this event. All data collected up to the date of consent withdrawal will be retained, but no further outstanding data collected. This will be made clear in the study information and consent form.

Statistical Analysis

Basic variables from CIED data

CIED data will be processed to create a new set of basic variables for analysis.

1. Mean daily physical activity (MDPA) – mean PA across dataset
2. PA intra-individual variability – as measured by:
 - Range
 - Interquartile range
 - Mean absolute deviation
3. PA surrounding NEHAs – multiple measures.

DOEDA = date of emergency department attendance; DOA = date of hospital admission; DOD = date of discharge; LOS = length of stay (DOD-DOA)

- Difference in PA from MDPA on DOEDA/DOA day -1, day -2, day-3, day-7, day -14
- Difference in PA from MDPA on DOEDA/DOD day +1, day +2, day+3, day+7, day +14
- ‘Time till PA recovery’ – time from DOEDA/DOD to day regained \geq MDPA

Descriptive analyses

All data will be stored and analysed using SPSS and ‘R’ statistical computing software. Basic descriptive statistics will be used to compare different sub-groups of participant (e.g. frail v non-frail). MDPA will be used to facilitate basic comparative analysis using a continuous variable. Determinants of MDPA will be calculated using univariate and multivariable analysis.

PA patterns

As demonstrated in *Figure 3* below, common activity patterns embedded within CIED PA data will be identified using clustering algorithms. Using these identified subtypes of PA as exposures in a longitudinal model with outcome NEHA, multilevel/hierarchical modelling methods (both classical and Bayesian approaches) will be utilised to investigate associations with outcome.

[figure not shown]

Figure 3

PA and major health events

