For this study, major health events are defined as NEHA episodes. Daily PA in the days leading up to NEHA episodes will be compared to a participant's MDPA, in order to define across the cohort when any observable change in PA is detected by this method. To explore trends in PA preceding NEHA episodes, a nested case control study will be constructed within the dataset, comparing trends in PA preceding NEHA episodes with general trends in PA before index times with no NEHA episodes. This will allow the creation of various 'PA markers' for diagnostic test evaluation methods (sensitivity/specificity, positive and negative predictive value). These PA markers will then be investigated to ascertain if they predict PA subtypes i.e. long-term behaviour patterns. We will also look at how these 'markers' superimposed on identified subtypes can be used to potentially personalise alert systems.

In a similar fashion, we will also explore PA trends following NEHA episodes. There is very little published data on 'recovery time' following hospitalisation episodes in an older population. This study is not powered to investigate this as a primary outcome, however we will measure 'time till PA recovery' following NEHA subtypes (A&E attendance and non-elective hospitalisation episodes), and examine determinants of this.

Risks to Study

Recruitment

A snapshot 'screening' audit using Cardex data in October 2016 found 341 potentially eligible patients on CIED annual follow-up at Manchester Royal Infirmary, an additional 150-250 patients at Wythenshawe are anticipated to be eligible. Recruitment will be undertaken by the PI. An 18-month period has been allocated for initial recruitment. Based on observational studies in similar population, we anticipate a take-up rate of from screening of between 60-80% (56).

Efforts made to maximise recruitment:

- Rigorous screening process
- Recruitment from existing clinical visits
- Low burden of assessment

In the event of lower than anticipated take-up, the recruitment window could be extended beyond 18 months to reach required sample size.

Missing data

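### Sample size: Table 1's 17% six-week NEHA risk conflicts nearly six-fold with the 0.34 visits per patient-year adopted beside it, so the stated 80% power at 150 participants is unsupported

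*Combined protocol and SAP*

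**What the plan says.** All the sizing inputs are in the section Sample Size Calculations. The calculation is described as "using exposure = low/decline in PA and outcome = NEHA within 6 weeks". In Table 1 the row "Percent of Unexposed with Outcome" is 17 under all four options. The exposed risk is 43% for RR 2.5 and 51% for RR 3, and the unexposed-to-exposed ratio is 4.4. The text adopts 150 participants, citing "using inputs: 95% significance, 80% power, RR 2.5-3, output: 88 – 198".

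The paragraph below the table takes an event rate from a cited heart failure study with 6 months of follow-up: 224 unscheduled visits "in 132 patients over 659 patient years, i.e. an annual rate of 34" per cent. For 150 participants contributing 150 patient-years it concludes that "we would expect to capture approximately 51 NEHA episodes from retrospective data collection".

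The analyses are described elsewhere. Under PA and major health events, "a nested case control study will be constructed within the dataset, comparing trends in PA preceding NEHA episodes" with index times that had no NEHA. Under PA patterns, the plan is a multilevel analysis: "Using these identified subtypes of PA as exposures in a longitudinal model with outcome NEHA".

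**The concern.** One section gives two event frequencies for the same outcome in the same cohort, and they differ by a factor of nearly six. A six-week risk of 17% among the lower-risk participants would make NEHAs common; 51 in 150 patient-years makes them uncommon. The sample size rests on the first figure and the expected event count on the second.

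The unit differs as well. Table 1 counts each participant once, with one outcome, whereas the planned analyses use NEHA episodes and repeated observations within a person.

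The stated power is the only justification for 150. Objective 4 sets out to confirm or refute that a fall in activity precedes NEHA, and Risks to Study ties any extension of recruitment to reaching the required number. If the power figure has no sound basis, a reader cannot tell in advance whether a null result at 150 would be informative.

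**Working it through.** **Inputs (all from Sample Size Calculations).** Unexposed risk 0.17; exposed risk 0.43 or 0.51; ratio 4.4, so the exposed share is q = 1/5.4 = 0.185; two-sided 5%; 224 visits, 132 patients, 659 patient-years; N = 150. Paired results below are for RR 2.5 / RR 3.

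**1. Table 1 reproduces.** With p̄ = (p1 + 4.4 p0)/5.4, the Kelsey number exposed is (z_α + z_β)² p̄(1−p̄)(5.4/4.4)/(p1−p0)². Fleiss uses the pooled variance under the null and separate variances under the alternative, without continuity correction. Totals are 5.4 times the number exposed.

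| Power | RR | Kelsey computed (printed) | Fleiss computed (printed) |
|---|---|---|---|
| 80% | 2.5 | 131 (133) | 143 (145) |
| 80% | 3 | 80 (81) | 87 (88) |
| 90% | 2.5 | 176 (177) | 197 (198) |
| 90% | 3 | 108 (108) | 119 (121) |

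The differences are rounding. The 198 in the quoted range is a 90%-power entry; the 80% entries run 88-145 (Fleiss) or 81-145 (both formulas).

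**2. The 51 reproduces.** 224/659 = 0.340 per patient-year; 0.340 × 150 = 51.0.

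**3. The two sets of inputs compared.**
- Table 1's overall six-week risk is (4.4 × 0.17 + 0.43)/5.4 = 21.8%, or 23.3% with 0.51. There are 150 × 365.25/42 = 1,304 six-week windows in 150 patient-years, so Table 1 implies about 285-304 windows with an event. Against 51 that is 5.6 to 6.0 times.
- In the other direction, 0.34 × 42/365.25 = 3.9% overall. Dividing by 1 + q(RR − 1) gives an unexposed risk of 3.06% / 2.85%, and an exposed risk of 7.65% / 8.56%.

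**4. Table 1's set-up at N = 150** (27.8 exposed, 122.2 unexposed). Power = Φ{[|p1−p0| − 1.96√(p̄(1−p̄)(1/n1+1/n0))] / √(p1(1−p1)/n1 + p0(1−p0)/n0)}.

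| Inputs | RR 2.5 | RR 3 |
|---|---|---|
| Table 1 as printed | 82% | 95% |
| 0.34 per year, six-week window | 26% | 34% |
| 0.34 per year, six-month window | 68% | 83% |

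The last row uses 0.34 × 0.5 = 17.0% as the whole-cohort risk, so the unexposed risk is 13.3% / 12.4%. These rows check the inputs; they do not estimate the study's power.

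**5. NEHA episodes as the unit.** The event-based (Schoenfeld) formula is power = Φ(√(D q(1−q)) ln HR − 1.96), with q(1−q) = 0.151, assuming that 18.5% of person-time is exposed.
- D = 51 independent NEHAs: 72% / 86%, minimum detectable HR about 2.75. For 80% power, 62 / 43 independent events are needed.
- Repeats: 224/132 = 1.70 visits per patient, reading the 132 as patients with a visit. Then 51/1.70 = 30 people, and counting one episode each gives 50% / 65%.

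**6. Open recruitment.** The plan's screening and take-up figures give (341 + 150) × 0.6 = 295 to (341 + 250) × 0.8 = 473 people, and so 100-161 NEHAs at 0.34 per year. Event-based power is then 95-99% / about 99% or more if episodes are independent. Counting one per person (59-95 people) it is 78-93% / 91-99%.

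**The case against.** The strongest reply is that the window label may be at fault and not the 17%. Six months at 0.34 per year is exactly 17.0%, and the cited study is described as having 6 months of follow-up. Most of the conflict then disappears: over 300 six-month windows, Table 1's overall risks give 65-70 windows with an event against 51. This is plausible but remains an inference, because the document attributes its inputs to other sources and never says what period the 17% covers. Nor would it fully repair Table 1, since 17% would then be the whole-cohort risk and not the unexposed risk.

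Second, 0.34 is offered only as a guide from stable heart failure, and all-cause attendances could be more frequent. That is fair; in that case the 51 needs restating.

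Third, each participant supplies many windows. Treating all 1,304 as independent gives 85% / 95%, but an assumed design effect of 2 gives 62% / 76%. The plan shows no such calculation.

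Fourth, recruitment does not stop at 150 (Screening and recruitment strategy) and can be extended (Risks to Study). This does limit the practical risk, but it supplies no basis for the power stated at 150.

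Fifth, several analyses are planned and none is named as primary, so the choice of unit is partly judgement. That stands, and it is why the figures in step 5 are conditional.

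**Conclusion.** The conflict is real and can be seen within one section: nearly six-fold between Table 1's six-week risks and the adopted event rate, with nothing to reconcile them. The stated 80% power at 150 is therefore unsupported.

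A reader might go further and infer that the study has only 26-34% power. The documents do not support that: the figure assumes one six-week window per participant, which is not the planned analysis, and takes the 0.34 as the correct input. On 51 independent NEHAs, power lies on both sides of 80% (72% / 86%), assuming 18.5% of person-time is exposed.

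Nor should 50% / 65% be read as a floor. It illustrates one allowance for repeat episodes, and it carries a ratio from a study with 6 months of follow-up over to 12 months of data. A larger ratio over the longer period would mean fewer than 30 people.

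It would also be wrong to say that Table 1 is miscalculated; its formulas reproduce and only the inputs conflict. The pairing of 80% power with a range ending at 198 is a separate slip that leaves 150 unchanged.

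**What to change.** Recruitment and the planned analyses stay as they are.

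(a) State the source and period of the 17%, and make Table 1, the outcome window and the 51 NEHAs agree. There are three ways:
- Keep six weeks and use about 3% in the unexposed.
- If 17% is a six-month figure, correct the window, treat 17% as the whole-cohort risk, and use 12.4-13.3% in the unexposed.
- If 17% per six weeks is right, restate the 51.

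(b) Restate power or the minimum detectable effect for 150 participants (about 51 NEHAs) with the NEHA episode as the unit, as in the nested case-control analysis. Include an allowance for repeat episodes within a person, and give the same figures for the larger number that open recruitment may yield.

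(c) Correct the range quoted for 80% power: either 88-145 (Fleiss; 81-145 for both formulas), or keep 88-198 and describe it as Fleiss at 80-90% power.

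The cost is a recalculation and some wording, with no extra patients, visits or data. The power stated for 150 may become less favourable.

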Although these studies have produced promising results, a recent review has highlighted that the predictive accuracy of PA in isolation remains poor (22). Trajectories have not been analysed, ‘normal’ remains unclear, and there has been no evaluation of the impact of ageing or frailty. Studies have also taken a narrow approach to data collection and outcome measures, capturing episodes of hospitalisation triggered by HF decompensation only, and death primarily due to HF. Bearing in mind people living with HF have on average four additional comorbidities (23), this study will take a holistic approach – measuring all-cause HCU (as measured by non-elective hospital attendance episodes).

Frailty

Frailty describes a state of reduced physiological reserve in older adults (2). Seen as a measure of biological ageing, frailty represents a vulnerability to physical and functional decline in the face of seemingly minor stressors – exemplified by the clinical presentation of ‘reduced mobility’ (often previously termed ‘acopia’). Three broad models of frailty exist in the literature: the phenotypic model, the cumulative deficit model, and pragmatic clinical assessments. The phenotypic model is based on pioneering work by Fried *et al.*, who described the five cardinal syndromic features of frailty: unintentional weight loss, exhaustion, weakness, slow walking speed, and low physical activity (24). This phenotypic model is based upon clinical assessment, and correlates well with markers of functional and physical health (25). Following on from this, Rockwood and colleagues developed the cumulative deficit model – a mathematical index based measure based on the accumulation of ‘symptoms, signs, diseases, and disabilities’ associated with ageing (26). This has progressed to an electronic frailty index (eFI), - a score based on 36 deficits constructed using over two thousand primary care read-codes (27). This model is population based, calculated remotely. In addition to these two models, a number of validated pragmatic clinical assessment methods exist, for example the Clinical Frailty Scale (28) and the Edmonton Frail Scale (29).

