For the PATTERn study, frailty assessments will be based on the Fried phenotypic model. This method was chosen as it demonstrates closest clinical correlation on an individual level, and is the most established in clinical and research practice (30). It also allows for the additional definition of ‘pre-frail’ i.e. patients at high risk of developing clinical frailty in the near future.

Considerations/Limitations

Accuracy of PA data from CIEDs

A number of reviews have examined the accuracy of various types of wearable activity trackers (31-34). PA is measured in CIEDs using an embedded single-axis accelerometer. Single-axis accelerometers only measure activity performed in the superior/inferior motion, thus are sensitive for postural movements such as walking, but less so for other forms of activity. For this reason single-axis devices may underestimate overall energy expenditure. With regard to accuracy in an older cohort, all activity monitors tend to be less accurate in participants with slower gait speed (33). In terms of differentiating 'active' versus 'sedentary' time, single-axis accelerometers have been shown to be accurate even in an older disabled cohort (35). A study by Pressler *et al.* 2013 (36) compared PA measurements from CIEDs with external tri-axial accelerometer in 73 participants (mean age 60±20 years). Correlation between the devices was strong (mean total daily activities, $r=0.64$; $p<0.001$) as was intra-individual correlation in the majority of participants (70%, $r>0.7$, $p<0.05$). However, Bland Altman plot analysis suggested significant variations in total daily activity measurements. Therefore, use of this data for pattern/trend analysis (as in this study) has been shown to be sufficiently accurate, however direct comparison of discrete PA measurements should be made with certain caveats.

Impact of CIED implantation on results

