encrypted trust USB stick. This will be immediately transferred onto the shared drive on an NHS desktop computer before being deleted from the USB stick. Personal details on the programmer will then be re-entered. This process takes approximately 1-2 minutes. The SPN-coded .pdd file will then be sent via secure end-to-end encrypted email to the technical team at the Medtronic Bakken Research Centre, Maastricht for processing. This SPN-coded data file is returned (following re-encryption) via secure email to the PI in an .xml file.

Self-report questionnaire (paper format)

Each participant will complete a study participant questionnaire (SPQ), a Medical Outcomes Study Questionnaire Short Form 36 Health Survey (SF-36) (45), and a Rapid Assessment of Physical Activity (RAPA) form (46). Participants will be asked to fill in the questionnaire whilst attending clinic and handed back to the researcher. We will allow a 2-week window period for participants to fill in the questionnaire in any circumstances where a participant is unable to do so in clinic (for example, running late for transport). Pre-paid envelopes to return the forms within this 2-week window will be provided. If the participant cannot perform this task independently, then the researcher will assist the completion of the questionnaire.

Physical frailty assessment

Frailty assessments will be based on the Fried phenotypic criteria as described above (24). Assessments will be performed by the researcher in a clinical room (except gait speed which will be measured in the corridor). See *Table 2* below.

Table 2: Frailty domains and criteria

Characteristic	Measure	Assessment	Interpretation
Weight loss	Weight, BMI (body mass index)	1. Single question: have you lost more thankg (10% body weight) in the last 4 years? 2. Height (cm) 3. Weight (kg)	One point in case of either: 1. Positive response to single question 2. $BMI < 18.5 \text{ kg/m}^2$ (47)
Muscle weakness	Grip strength (48, 49)	Jamar J00105 hydraulic hand dynamometer Southampton protocol (49)	One point if 'low' Cut-offs stratified by gender and BMI:

			
Men
 
BMI \leq 24: \leq 29kg
 
BMI 24.1–26: \leq 30kg
 
BMI 26.1–28: \leq 30kg
 
BMI \geq 28: \leq 32kg
 
Women
 
BMI \leq 23: \leq 17kg
 
BMI 23.1–26: \leq 17.3kg
 
BMI 26.1–29: \leq 18kg
 
BMI \geq 29: \leq 21kg

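### The Table 2 weight-loss item gives a frailty point for any loss of more than 10% in 4 years, although the phenotype the protocol adopts specifies unintentional loss

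*Combined protocol and SAP*

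**What the plan says.** Four places in the combined protocol and SAP bear on this.

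- **Rationale/Background, Frailty.** The five features of the phenotype are "unintentional weight loss, exhaustion, weakness, slow walking speed, and low physical activity". Later in the section the study adopts this model: "frailty assessments will be based on the Fried phenotypic model".
- **Considerations/Limitations, Validity of frailty assessments.** The criterion is restated without any reference to intent: "Significant weight loss within the criteria is defined as over 10% body weight in the preceding four years", or a measured BMI below 18.5 kg/m2. The section accepts that weight loss may be the less reliable domain in heart failure, and defends it on fluid status: "These criteria would not tend to capture patients whom have lost weight simply due to diuresis".
- **Data collection process, Physical frailty assessment.** The text refers back to the background: "Frailty assessments will be based on the Fried phenotypic criteria as described above (24".
- **Table 2 (Frailty domains and criteria), weight-loss row.** The participant is asked about loss of more than a stated number of kg, glossed as "10% body weight) in the last 4 years". The point is given for either "Positive response to single question" or BMI below 18.5 kg/m2.

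Below Table 2, three or more criteria are classed as frailty, one or two as pre-frail, and none as no frailty.

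**The concern.** The methods claim to apply the criteria set out in the background, but the scored question leaves out a qualifier that is part of one of them. A participant who lost more than 10% of body weight on purpose within four years answers yes truthfully and gets the point, although the described phenotype would not give it.

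Frailty is the moderator in objective 3 and supplies the frail versus non-frail comparison given as an example under Descriptive analyses. A point scored for something other than the intended construct is misclassification in that variable. Analysis cannot repair it. The Summary of data to be collected lists no weight history, dieting or intent item, and current height and weight do not show why weight was lost.

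**Working it through.** The plan gives no figure to reproduce here. The check is a comparison of wording, followed by a count of how one extra point moves the category.

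**Step 1: the four places compared.**

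| Place | Weight-loss criterion | Intent mentioned? |
|---|---|---|
| Background, Frailty | Unintentional weight loss | Yes |
| Validity of frailty assessments | Over 10% in four years, or BMI below 18.5 kg/m2 | No |
| Table 2, question | More than 10% in 4 years | No |
| Table 2, scoring rule | Yes to the question, or BMI below 18.5 kg/m2 | No |

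Physical frailty assessment points back to the first row and then applies the third and fourth. No departure from the described phenotype is stated.

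**Step 2: is deliberate loss dealt with elsewhere?** Diuresis is the only alternative cause discussed. The argument there is that the criteria would not tend to pick up loss due to diuresis alone. It does not carry over to deliberate loss, which can build up over four years. The BMI route can add a point but never removes one.

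**Step 3: effect of one point on the category.** Let k be the number of the other four criteria met. Take a participant with BMI of 18.5 kg/m2 or more, so that the point rests on the question alone.

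| k | Patterns of the other four items | Without the point | With the point | Category changes? |
|---|---|---|---|---|
| 0 | 1 | No frailty | Pre-frail | Yes |
| 1 | 4 | Pre-frail | Pre-frail | No |
| 2 | 6 | Pre-frail | Frailty | Yes |
| 3 | 4 | Frailty | Frailty | No |
| 4 | 1 | Frailty | Frailty | No |

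There are 1 + 4 + 6 + 4 + 1 = 16 patterns, and 1 + 6 = 7 of them change category. These are unweighted counts of possible patterns, not prevalences. They show where the category is sensitive to the point, not how many participants are there.

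**Step 4: number of participants.** This would need the share answering yes, the share of those losses that were intended, and the distribution of k among those people. The documents give none of the three.

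**The case against.** The strongest reply is that the background passage summarises the literature, while Validity of frailty assessments and Table 2 state the study's own rule, and those two agree. The assessments are said to be based on the phenotype, so the any-loss version could be a deliberate simplification. It could be, but Physical frailty assessment says the criteria are those already described and cites the same source, and no departure is stated or justified. What stands is that a justified adaptation would be an acceptable answer.

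A second reply is that the case report form and participant questionnaire are listed as supporting documents but were not supplied. Table 2 leaves the kg value blank and may paraphrase the wording used, and the researcher assesses participants in person. This stands as a limit: the documents show that intent is absent from the protocol's question and scoring rule, not that it is never asked in practice.

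A third reply is that this is one item of five in a moderator. It leaves the sample size, the activity measure, the ascertainment of hospital attendances and objectives 1, 2 and 4 untouched. That is correct and bounds the importance.

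A reader might also infer three stronger things that the documents do not support.

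- *Deliberate slimming counts as frailty.* It earns one point. Alone that gives pre-frail; it gives frailty only with exactly two other criteria.
- *Those mis-scored are the more active participants, so the frail versus non-frail contrast is weakened.* Nothing in the documents shows this. A fit dieter meeting no other criterion would move to pre-frail, and a contrast split at three criteria would not change. The plan does not say whether frailty enters the analyses as two levels, three levels or a count.
- *A number of participants can be given.* Assuming that 10-20% answer yes and 25-50% of those losses were intended gives 0.10 x 0.25 = 2.5% to 0.20 x 0.50 = 10%, or 3.75 to 15 of 150. Both rates are assumed without a source in the documents, and the result counts points wrongly awarded, not categories changed.

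**Conclusion.** The inconsistency is real. The protocol adopts a phenotype with unintentional weight loss, says it applies the criteria as described, and then scores any loss of more than 10% in 4 years. Following the written rule gives deliberate loss one frailty point, and no other listed data item allows the point to be removed later.

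The consequence is limited to one point. The category changes only at zero other criteria (no frailty to pre-frail) or two others (pre-frail to frail). The number of participants affected, and the direction of any bias in the objective 3 moderation analysis, cannot be determined from the documents. The conclusion assumes that the recording form follows the Table 2 wording. It is worth correcting because the remedy is small and the missing information is not otherwise collected; it does not threaten the study as a whole.

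**What to change.** Reword the Table 2 item to ask whether the participant has unintentionally, that is without dieting or trying to, lost more than the stated kg (10% of body weight) in the last 4 years. Score the point only for unintentional loss or BMI below 18.5 kg/m2. Use the same definition in Validity of frailty assessments and on the form where the answer is recorded. If that form already asks about intent, only the protocol text needs correcting.

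If the any-loss version is a deliberate adaptation, state and justify it in Physical frailty assessment, still record intent, and add a sensitivity analysis of the frailty results that scores only unintentional loss.

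The cost is a few words in one question and matching edits to the text and form, plus one extra analysis if the adaptation is kept. No added visit or procedure is needed.
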